### **IV. Study Design**

- a. Experimental Design: Patients that meet the inclusion/exclusion criteria will be eligible for participation in the study. The design will be a single blinded format where the surgeon will be aware of what treatment the patient will receive (Control vs. Intervention). The patient will not be informed of what arm of treatment they were selected for. Block randomization will be utilized to place an equal number of patients into both groups.
- b. Study Population: Patients undergoing arthroscopic shoulder surgery with long head of the biceps tendon pathology.
- c. Sample size determination and power analyses:  
Based on previous studies, it is assumed that the pre-ASES score for all patients undergoing biceps tenodesis is approximately 45. At 1 year post surgery, the standard of care group will increase to 85 (Mean difference = 40, STD=18). It is hypothesized that the treatment group with anatomical fixation will increase to approximately 93 (Mean difference = 48, STD=18).

The necessary sample size was calculated using 80% power of rejecting the null hypothesis (that there is no difference in change in ASES scores between the two groups of interest), when the population mean difference in ASES is  $\Delta 1 - \Delta 2 = 48 - 40 = 8$ , with a standard deviation of 18, and with a significance level (alpha) of 0.05. This power and sample size calculation was computed using a two-sided two-sample equal-variance t-test.

To achieve this power, at least 81 patients will need to be enrolled in each group. Patients will only be randomized once to this study. If a patient has a repeat surgery, that case will not be eligible for randomization.

- d. Study outcomes/endpoints
  - i. Study endpoint will be decided based on the power analysis that was calculated by the research team biostatistician.
  - ii. Data collected:
    1. Demographics: Name, MRN, age, sex, hand dominance, ethnicity, profession, BMI

2. Clinical Factors: Indication for surgery, procedures performed, past medical history of upper extremity pathology
3. Medical History: Myocardial infarction, congestive heart failure, peripheral vascular disease, transient ischemic attack or cerebrovascular accident, dementia, chronic obstructive pulmonary disease, connective tissue disease, peptic ulcer disease, liver disease, diabetes, hemiplegia, chronic kidney disease, solid tumor, leukemia, lymphoma
4. Measurements: (in mm)

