2. During the diagnostic arthroscopic shoulder scope, the long head of the biceps is inspected for any instability or tendinopathy, which would be an indication to perform tenotomy at the junction of the supraglenoid tubercle with arthroscopic scissors
  - a. If Control group: Bicep tenotomy will occur now
3. The patient will undergo all other indicated arthroscopic portions of the case (i.e. rotator cuff repair, subacromial decompression, rotator interval release, etc.)
4. At the conclusion of the arthroscopic portion of the case, the patient's arm will be placed with the elbow at 90 degrees of flexion and neutral forearm rotation. ***The trochar in the anterior shoulder portal and the arthroscope in the posterior shoulder portal will be left in the glenohumeral joint momentarily. The arthroscopic light will be shut off temporarily. Both will be secured to the shoulder using sterile ioban to maintain a good water seal & ensure that both are kept in the correct position for tenotomy later***
5. The standard mini-open subpectoral approach will be made along the anterior axillary fold
6. Full thickness skin flaps are developed down to muscular fascia

7. The biceps fascia is opened and the pectoralis major tendon is retracted superiorly
8. *The myotendinous junction of the long head of the biceps tendon and its location within the intertubercular groove will be marked using electrocautery*
9. *The surgeon will then turn back to the glenohumeral joint, remove the ioban, turn the arthroscope back on, then perform the biceps tenotomy. All instrumentation will be removed from the glenohumeral joint at this time*
10. *The surgeon will then turn to the mini-open subpectoral incision that was previously made and the long head of the biceps tendon will be retrieved*
11. **A ruler will be used to measure the entire length of the long head of biceps tendon from origin to end of tendon fibers, origin to beginning of tendon fibers, and width of the tendon**
12. **The arthroscopy camera will be used to take pictures of the biceps tendon at the myotendinous junction next to a ruler for scale**
  - a. Per standard protocol, these arthroscopic pictures will be inserted into the electronic medical record. This data will be retrospectively collected by a member of the research team.
13. The tendon is tagged with a running, locking number 2 fiberwire suture at the mid substance of the myotendinous junction *using the previously made electrocautery marks to set the tension*

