## VI. Safety Monitoring Plan

### a. Definition of adverse events, serious adverse events

- i. All surgical interventions are accompanied by a risk of blood loss, infection, and damage to surrounding structures. Patients will be advised that post-op pain and stiffness is expected and normal. If this surgery is not successful, there may be need for additional surgeries. If the patient undergoes rotator cuff repair in addition to biceps tenotomy and tenodesis, there are risks that the rotator cuff repairs may fail to heal or even retear. Symptomatic retears may require further operative intervention. Scar tissue accumulation may also require further operations. All of these risks are routine risks associated with arthroscopic biceps tenotomy and

tenodesis with or without rotator cuff repair. The only known possible risk specific to this research study will be an additional 1-2 minutes under anesthesia for those selected for the intervention group. This risk is considered low with minimal risk to the patient. There is minimal risk of loss of patient confidentiality. All data will be recorded and stored in the password protected Loyola R: drive, then will be de-identified prior to data analysis.

- b. What procedures will be used to monitor subject safety?
  - i. As with all patient interactions, safety will be prioritized by all participants involved in caring for the patient. Our research project does not incur any increased safety concerns. However, due to the nature of research, participants in our study will inherently receive more attention because of increased interactions with members of the research team. If any concerns, suggestions, or questions arise during our research project, they will immediately be brought to the attention of the principal investigators of the study.
- c. Who (list names) will identify, document, and report adverse events?
  - i. Adverse event identification will be the responsibility of each member of the research team, specifically, [name] and [name]. These events will be reported promptly to the IRB office.
- d. What are the stopping rules with regard to efficacy and safety?
  - i. All patients involved in the study will be allowed to withdraw at any time. Consent may be revoked at any time prior to completion of the study, which is expected to be a duration of one year. All members of the research team will be held responsible for notifying the sponsors of the study ([name] & [name]) if patient safety is compromised.

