### **VIII. Statistical Analysis Plan**

The primary aim of assessing change in the ASES score from baseline to post-surgery between the control and intervention groups will be assessed using a student's t-test, as indicated in the study design.

In addition, longitudinal mixed effects models will be used to estimate changes in ASES scores, over all time-points using a random effect for surgeon. Other relevant patient characteristics such as age, sex, and Charlson score will be included to explore the adjusted relationship of the intervention and outcomes over time.

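### The primary ASES t-test ignores whether a cuff repair was indicated before surgery, which costs a little precision that one covariate could recover

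*Combined protocol and SAP*

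**What the plan says.** - **Case mix.** Section V.d.iv, step 3: "The patient will undergo all other indicated arthroscopic portions of the case". Rotator cuff repair, subacromial decompression and rotator interval release are given as examples. The eligibility criteria in V.a do not restrict cuff disease.
- **Outcome risk.** Section VI.a says that for patients who also have a cuff repair "there are risks that the rotator cuff repairs may fail to heal or even retear", and that symptomatic retears may need another operation.
- **Data.** Section IV.d.ii lists the clinical factors to be collected: "Indication for surgery, procedures performed, past medical history of upper extremity pathology".
- **Allocation.** Section V.b uses 1:1 blocks stratified by surgeon only. The surgeon is told the arm before surgery starts.
- **Analysis.** Section VIII tests the change in ASES with a Student's t-test. Mixed models over all time points, with a random effect for surgeon, come in addition, and for these "Other relevant patient characteristics such as age, sex, and Charlson score will be included to explore the adjusted relationship". Cuff status is named in neither analysis.

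**The concern.** ASES is not specific to the biceps. Half the score is pain, and the functional items include reaching a high shelf, lifting overhead and throwing. A patient whose cuff is repaired in the same operation may well change by a different amount from a patient with tenodesis alone, whatever the tensioning method. If so, that difference sits in the error term of an unadjusted t-test. Stratifying by surgeon does not remove it, and neither do the three named covariates, none of which describes the shoulder.

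At stake is the precision of the primary estimate. The design has little slack: 81 per arm is the smallest number that gives 80% power, and section IV.c shows no allowance for dropout.

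**Working it through.** **1. The plan's own figure.** Inputs from section IV.c: changes of 48 and 40 points (difference 8), "with a standard deviation of 18, and with a significance level (alpha) of 0.05", "using 80% power of rejecting the null hypothesis", "computed using a two-sided two-sample equal-variance t-test". The exact t-test calculation gives 80.44, rounded up to 81 per arm. Power at 81 is 80.3%. The stated sample size reproduces.

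**2. Assumptions.** The documents give neither p, the share of patients with a cuff indication, nor d, the difference in mean ASES change by cuff status. Both are assumed below.

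**3. Formulas.**
- Share of variance explained: R² = p(1−p)d²/18²
- Residual SD after adjustment: 18·√(1−R²)
- Power: the same t-test calculation, with the residual SD in place of 18

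**4. Results at 81 per arm.**

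| p | d (points) | R² | Residual SD | Power |
|---|---|---|---|---|
| – | 0 (as planned) | 0 | 18.00 | 80.3% |
| 0.2 | 3 | 0.4% | 17.96 | 80.4% |
| 0.5 | 3 | 0.7% | 17.94 | 80.5% |
| 0.2 | 5 | 1.2% | 17.89 | 80.8% |
| 0.5 | 5 | 1.9% | 17.83 | 81.0% |
| 0.5 | 10 | 7.7% | 17.29 | 83.3% |

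In the last row R² = 0.25 × 100/324 = 0.077, and 75 per arm would give 80% power.

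**5. Confidence interval, last row.** Unadjusted: 1.96 × 18 × √(2/81) = 5.54 points. Adjusted: 1.96 × 17.29 × √(2/81) = 5.33 points. The half-width narrows by about 0.2 points.

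**6. Chance imbalance is the same quantity.** With p = 0.5, the between-arm difference in cuff share has SD √(2 × 0.25/81) = 0.079. With d = 10 this moves the estimate by 0.79 points (1 SD), or 1.54 points at the 95% limit. The variance of that movement is 100 × 2 × 0.25/81 = 0.62. The variance of the unadjusted arm difference is 2 × 324/81 = 8.00, and 0.62/8.00 = 7.7%, which is R² again. The t-test's standard error therefore already contains the imbalance.

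**7. Indication is not repair.** If d = 10 applies to actual repair, and the preoperative indication identifies repair with an assumed 80% sensitivity and specificity at p = 0.5, the difference by indication is 10 × (0.8 + 0.8 − 1) = 6 points. Then R² = 0.25 × 36/324 = 2.8%, and power is 81.4% instead of 83.3%.

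**The case against.** **The gain may be negligible.** This stands in part. To explain even 5% of the variance at p = 0.5, cuff status must shift ASES change by about 8 points (√(0.05 × 324/0.25) = 8.0), as much as the trial's whole target effect. Section VI.a makes a link with outcome plausible. It gives no effect on ASES change, so calling cuff status a strong predictor would go beyond the documents. The gain is also computed against no adjustment at all; what cuff status adds beyond baseline ASES, age, sex and Charlson score is unknown and may be less.

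**The covariate list is open.** It is introduced as examples, so cuff indication is not ruled out. But an open list does not prespecify anything, and it belongs to the exploratory models. A covariate added only there leaves primary power at 80.3%, because the t-test takes none.

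**The variable is not defined yet.** This stands. Section IV.d.ii names the indication for surgery without a cuff category or a time of recording. A cuff variable fixed before allocation is inferred from that field. Tears found only at arthroscopy would be missed.

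**Why not adjust for the repair itself?** Step 2 of the surgical sequence already differs by arm, and step 3, where the other procedures are done, follows it. Procedures performed are thus settled by a surgeon who knows the arm, and adjusting for them could introduce bias.

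**Conclusion.** The point holds as a modest, avoidable loss of precision in the primary analysis. Under the assumptions shown, power rises by about 0.1 to 0.7 percentage points for a 3 to 5 point cuff difference, and by 3 points for a 10 point difference at a 50% share. Misclassification or overlap with other covariates would reduce this. The direction rests on cuff status predicting ASES change, which the documents make plausible but do not quantify.

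A reader might infer that mixing the two kinds of operation biases the comparison or makes the sample size wrong. The documents do not support this: allocation is random within surgeon, the t-test is valid without covariates, and 81 per arm is right for that test. A reader might also count chance imbalance as a second harm beside the wider interval. Step 6 of the working shows that they are one variance component. The change is worth making because it is cheap, not because the planned test fails.

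**What to change.** In section VIII:

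1. Make the primary comparison an ANCOVA of ASES, or the equivalent arm contrast from the mixed model, with arm, baseline ASES, surgeon and preoperative cuff indication (yes/no).
2. Define cuff indication as a yes/no code taken from the recorded indication for surgery and fixed before the arm is revealed.
3. Keep the unadjusted t-test as a supportive analysis.
4. Do not adjust for procedures performed. Report them by arm.

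The cost is coding one yes/no variable from a field already collected, with its timing locked, and one degree of freedom for it. No additional patients or visits are needed.

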14. The tendon is shortened
15. The sutures from the biceps are passed through the Arthrex cortical button
16. The pectoralis major tendon is retracted and 2 centimeters proximal to the distal insertion a unicortical bone tunnel is drilled in the bicipital groove with a 3.2 millimeter drill
17. The wound is irrigated and the biceps button is threaded into this tunnel and then flipped. The suture is tensioned, securing the biceps against the groove
18. The skin is closed in the usual fashion

e. Study Assessments and Activities

- i. If indicated, patients will undergo biceps tenodesis, as described above
  1. Standard protocol for [name] and [name] is for patients to follow up at 2 weeks, 6 weeks, 3 months, and 6 months after surgery.
    - a. A member of the research team will be at the office visit to obtain an ASES score prior to surgery and will contact patients via phone at 2 weeks, 6 weeks, 3 months, and 6 months and one year after surgery.

- b. A member of the research team will retrospectively collect history and physical examination data using [name] or [name] notes (Complications, Range of motion, strength, special shoulder or elbow physical exam tests).
2. Once the patient has completed their 6 month follow up appointment, all identifiable data from that patient will be deleted from all research records.

[figure not shown]

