## **VII. Plan for patient identifiers and information**

- a. Plan to protect patient identifiers for improper use and disclosure
  - i. All patient health information (PHI), demographics and sensitive data will be kept on the Loyola provided secure server in an assigned password protected folder located on the R: drive. All paper records, if any, will be kept in a locked cabinet in the offices of the principal investigator.
- b. Removal of patient identifiers and record retention
  - i. Upon completion of the study, electronically stored patient identifiers will be deleted from the R: drive and any paper records will be disposed of using Loyola Medical Center approved shred bins for such purpose.
- c. Individuals with access to protected health information
  - i. Only research team members listed on the protocol will be granted access.
- d. Summary of the use of the data
  - i. Data will be collected in a prospective manner, statistically analyzed and formatted for presentation at regional or national surgical meetings and/or publication in peer reviewed surgical/medical journals.

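### Identifiers are to be deleted after the 6-month visit, about six months before the one-year ASES call on which the sample size rests

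*Combined protocol and SAP*

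**What the plan says.** The document gives two times for removing identifiers.

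- Section V.e.i.2 (Study Assessments and Activities), patient by patient: "Once the patient has completed their 6 month follow up appointment, all identifiable data from that patient will be deleted from all research records".
- Section VII.b (Removal of patient identifiers and record retention), for the study as a whole: "Upon completion of the study, electronically stored patient identifiers will be deleted from the R: drive".

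Section VI.a adds: "All data will be recorded and stored in the password protected Loyola R: drive, then will be de-identified prior to data analysis". Section VI.d adds: "Consent may be revoked at any time prior to completion of the study, which is expected to be a duration of one year".

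On follow-up, section V.e.i.1 states that the surgeons' standard protocol "is for patients to follow up at 2 weeks, 6 weeks, 3 months, and 6 months after surgery". Item 1.a beneath it says that a member of the research team "will contact patients via phone at 2 weeks, 6 weeks, 3 months, and 6 months and one year after surgery", and section V.a.iii (Screening procedures) repeats this. Section V.a.iii also says, separately, that the questionnaire is repeated at 6 months.

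On the outcome, section IV.c names one post-operative time: "At 1 year post surgery, the standard of care group will increase to 85 (Mean difference = 40, STD=18". The intervention group is assumed to change by 48 points with the same SD, and the section concludes: "To achieve this power, at least 81 patients will need to be enrolled in each group". Section VIII compares the change from baseline to an undated post-surgery time and refers back to the study design.

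**The concern.** Within section V.e.i, one item requires a research call at one year and the next removes all identifiable data from all research records about six months earlier. A team that follows the deletion rule exactly could not reliably reach patients at one year from its own records, nor attach a 1-year score to the right baseline and arm. A team that follows section VII.b could do both.

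The link matters as much as the contact. The primary outcome is a within-patient change compared between arms, so a 1-year score without its baseline and allocation is unusable. The mixed model over all time points in section VIII needs the same link.

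Deletion cannot be undone, and it would start with the first patient to complete the 6-month visit, long before anyone opens the data for analysis. Staff who instead keep identifiers in order to make the call would breach the confidentiality commitment in section V.e.i.2.

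**Working it through.** **1. Order of events for one patient**

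| Time after surgery | Event | Section |
|---|---|---|
| 2 weeks, 6 weeks, 3 months | Clinic visit and ASES call | V.e.i.1 and 1.a |
| 6 months | Last listed standard visit; ASES call | V.e.i.1 and 1.a |
| After the 6-month visit | All identifiable data deleted from all research records | V.e.i.2 |
| 1 year | ASES call; the time used for the sample size | V.e.i.1.a; IV.c |
| Study completion | Electronic identifiers deleted | VII.b |

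Deletion comes about 12 − 6 = 6 months before the call. No standard visit is listed after 6 months to back up the call.

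**2. Does anything survive that would restore the link?** The data list in section IV.d.ii holds name and medical record number as direct identifiers and no study number. No section of the available text describes a coded key kept after deletion.

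**3. The plan's own sample size.** Inputs from section IV.c: changes of 48 and 40, SD 18, two-sided alpha 0.05, power 80%, two-sample equal-variance t-test. Equal allocation is from section IV.a.

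- Difference = 48 − 40 = 8; standardised effect d = 8/18 = 0.444.
- Power for n per group comes from the noncentral t distribution with 2n − 2 degrees of freedom and noncentrality d × √(n/2).
- Solving for 80% power gives n = 80.44, rounded up to 81. The stated figure reproduces.
- At n = 81 the noncentrality is 0.444 × √40.5 = 2.83 and power is 80.3%. At n = 80 power is 79.8%.

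Section IV.c adds no allowance for missing 1-year scores, so the loss of one patient per group already takes power just below 80%.

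**4. What lost scores would cost.** The documents give no expected share of linked scores. The shares below are assumptions, with equal loss in both arms and loss unrelated to outcome. Effective n = 81 × share.

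| Share linked (assumed) | n per group | Power for 8 points | Difference detectable with 80% power |
|---|---|---|---|
| 100% | 81 | 80.3% | 8.0 |
| 90% | 72.9 | 76.0% | 8.4 |
| 75% | 60.75 | 68.1% | 9.2 |
| 50% | 40.5 | 50.6% | 11.3 |

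If the 6-month rule were applied to every patient who completes that visit, none of those patients' 1-year scores could be linked from the research records.

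**The case against.** The strongest points on the other side are these.

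- **The two deletion rules can be reconciled.** Section VII.b can be read as a final clean-up after rolling deletion by patient, and de-identifying before analysis (section VI.a) satisfies either rule. This is fair, and it softens the conflict between V.e.i.2 and VII.b. It does not touch the clash between the 6-month deletion and the one-year call, which lies inside section V.e.i.
- **The year in section VI.d is ambiguous.** It does not say whether it means each patient or the whole study. It fits VII.b better than V.e.i.2 but does not settle the matter.
- **Section V.a.iii repeats the questionnaire at 6 months, and section VIII gives no time.** Follow-up might therefore have been meant to end at 6 months. However, the schedule that includes one year already includes 6 months, so that sentence is compatible with both readings, and the sample size names only 1 year.
- **Contact and allocation may be recoverable.** Deletion is from research records; the medical record remains, and arm might be rebuilt from the randomization list, which is used in order of surgical start time. So near-total loss is a worst case. Rebuilding the link in that way would, however, defeat the deletion rule.
- **The power table is generic.** The rule is close to all-or-nothing, and nothing in the documents produces 90%, 75% or 50%. This stands: the table shows sensitivity and is not a forecast.
- **A key may be described elsewhere.** A figure follows the deletion sentence but is not shown, and no assessment schedule appears under section V.e.iii in the available text. That no key exists can be said only of the text available.

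**Conclusion.** The concern holds. The deletion rule in section V.e.i.2 is incompatible with the one-year ASES call in the same section and does not match section VII.b. It must be corrected, because following it as written would irreversibly cut the link between the 1-year score and the baseline and arm.

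Confidence is high on the textual conflict and lower on the amount of data that would be lost, which depends on the rule staff follow and on whether an undescribed key exists. The power figures assume the protocol's difference of 8 and SD of 18, and equal loss in both arms unrelated to outcome. The sample size calculation itself is correct, and 81 per group need not change on this account.

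**What to change.** 1. **Section V.e.i.2:** remove the sentence so that section VII.b governs, or replace it with wording such as: *Identifiers and any linkage key are kept until the patient's one-year ASES has been obtained and verified, or its window has closed, and are then deleted.* The available text defines no window for the one-year call, so one must be added if this wording is used.
2. **Section VII.b:** define completion of the study in the same terms.
3. **Section V.a.iii:** align the separate 6-month statement with the full follow-up schedule.
4. **Consent form:** check that its wording on data retention agrees. It was not available for this review.
5. **Section VIII, a related clarification on which the conclusion does not depend:** name the change in ASES from baseline to 1 year as the single primary endpoint, with the other time points secondary. This states what the reference to the study design appears to intend.

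The cost is protocol wording and an IRB amendment, plus a consent update if its retention text differs. Identifiers stay about six months longer on the same password-protected drive, a small added confidentiality exposure. No patients or visits are added.
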